CPK will be monitored at baseline and monthly during treatment or as clinically indicated. Instructions for Dose Modification for elevated CPK and rhabdomyolysis are included in [Table 12](#) in Section 6.1.1.

Photosensitivity (when Administered with Vemurafenib)

No evidence of phototoxicity has been observed with cobimetinib as a single agent. However, photosensitivity was observed on Study GO28141 with a higher frequency in the cobimetinib plus vemurafenib arm versus the placebo plus vemurafenib arm (46% vs. 35%, respectively). The majority of events were Grades 1 or 2, with Grade \geq 3 events occurring in 4% of patients in the cobimetinib plus vemurafenib arm versus 0% in the placebo plus vemurafenib arm. Grade \geq 3 photosensitivity events in the cobimetinib plus vemurafenib arm were treated with primary topical medication in conjunction with interruption of study agents. Refer to Section 6.1.1 for photosensitivity management guidelines.

Pneumonitis

Events of pneumonitis have been reported in cobimetinib clinical studies. Most reported events were considered non-serious and of low-severity grade. In the Phase III Study GO28141, pneumonitis events were reported more frequently in patients treated with cobimetinib plus vemurafenib than placebo plus vemurafenib (1.6% vs. 0.4%, all grades). There were no reported Grade \geq 3 events in either study arm. Serious adverse events were reported in 2 patients (0.8%) treated with cobimetinib plus vemurafenib.

3.10.2.2 *Potential Risks Associated with Cobimetinib*

Liver Laboratory Abnormalities and Severe Hepatotoxicity

Liver laboratory test abnormalities, including increases in ALT, AST, and ALP, have been reported as adverse events and serious adverse events in patients treated with cobimetinib plus vemurafenib.

In the Phase III Study GO28141, liver laboratory test abnormalities reported as Grade ≥ 3 adverse events occurred more frequently in patients treated with cobimetinib plus vemurafenib than placebo plus vemurafenib (20.5% vs. 15.1%, respectively).

Generally, elevations in liver laboratory tests were managed effectively with dose modification guidelines. In both study arms, the majority of Grade ≥ 3 liver laboratory test abnormalities resolved.

Impaired Female Fertility

There is a potential for effects on fertility and embryo-fetal toxicity based on results from nonclinical studies.

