Patients will be monitored weekly for safety during the first 8 weeks and then every 4 weeks starting with Cycle 3 and also as needed until 28 days after the last dose of study treatment or until initiation of other anti-cancer therapy, whichever occurs first. All unresolved adverse events and serious adverse events will be followed until the events are resolved or stabilized, the patient is lost to follow-up, or it has been determined that the study treatment or participation is not the cause of the adverse event or serious adverse event. Dermatologic, head and neck evaluations, and chest CT scans will be conducted according to the local standard of care after patient discontinues study treatment, withdraws consent, dies or is lost to follow-up, whichever occurs earliest. Please see Section 5.3.4.6.

Definitions of DLTs have been designed to keep the degree and frequency of severe toxicity observed in this study within acceptable limits for Phase I trials in oncology.

General safety assessments will include serial interval histories, physical examinations, and specific laboratory studies, including serum chemistries and blood counts (see Section 5.3.4, Table 9 for the list and timing of study assessments).

All serious adverse events, protocol-defined adverse events of special interest, DLTs, and Grade 3 and 4 adverse events during the DLT assessment window will be reported in an expedited fashion (see Section 7.1.1.4). In addition, the Medical Monitor and the investigators will review and evaluate observed adverse events on a regular basis.

Patients who have an ongoing treatment-related adverse event upon study completion or at discontinuation from the study will be followed until the event has resolved to baseline grade, the event is assessed by the investigator as stable, new anti-tumor treatment is initiated, the patient is lost to follow-up, the patient withdraws consent, or it has been determined that study treatment or participation is not the cause of the adverse event.

See Table 9 and Section 5.3.4 (Assessment of Safety) for complete details of the safety evaluation for this study.

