1. Informed consent must be obtained before any study specific screening assessments are performed. Screening assessments are to be performed within 28 days prior to Day 1 of Cycle 1 unless otherwise noted. Assessments performed as standard of care within the screening window may be used for screening. Screening exams for ECG, hematology, chemistry, coagulation, urinalysis, and pulse oximetry must be performed within 14 days of first dose. Note: All study patients who were not previously treated with vemurafenib must have melanoma tissue tested for BRAF^{V600} mutation using the cobas[®] 4800 BRAF V600 Mutation Test. Testing requires a formalin-fixed paraffin-embedded (FFPE) tumor block or unstained sections. A screening window of 42 days prior to Cycle 1, Day 1 will be allowed to test for the BRAF^{V600E} mutation in patients without prior exposure to vemurafenib only. Other screening assessments can commence only after a positive test result is documented and a slot is available in an open cohort of either the dose-escalation or cohort-expansion phase. For patients without prior exposure to vemurafenib, the 28-day window (Day -28 to Day -1) for performing screening assessments begins at the time the first screening assessment is performed after documentation of BRAF^{V600E} mutation-positive tumor tissue.
2. Physical exam will be performed during screening and subsequently at each study visit. The frequency of each study visit should be performed in accordance with the local standard of care. After initial screening physical exam, a limited physical exam, a symptom-directed exam that contains an evaluation of the oropharynx, lungs, heart, abdomen, and skin will be performed. Patients will be asked about skin and vision changes at each symptom-directed physical exam. Assessments must be done before study drug dosing, where applicable.
3. ECOG, weight, and vital signs, which include temperature, heart rate, respiratory rate, and systolic and diastolic blood pressures while the patient is in a seated position, will be collected when a physical exam is performed in accordance with standard of care. Height will be collected only at screening/baseline.

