7. Chemistry includes glucose, BUN, creatinine, sodium, potassium, chloride, magnesium, bicarbonate, phosphate, calcium, total protein, albumin, total bilirubin, direct bilirubin, ALP, LDH, CPK, uric acid, AST, and ALT. Note: Patients who exhibit CPK elevation coincident with cobimetinib treatment should have measurement of MB fraction, if there is a clinical suspicion of possible myocardial injury or in the case of prolongation of the QTc interval. Frequency of chemistry assessments after Cycle 4 should be performed in accordance with the local standard of care.
8. Urinalysis is required only at screening and includes specific gravity, pH, glucose, protein ketones, blood, and microscopics (RBC, WBC, casts, and crystals).
9. For women of childbearing potential, including premenopausal women who have had a tubal ligation, a serum pregnancy test is required at screening (within 7 days prior to C1D1) and should be performed in accordance with the local standard of care while the patient is receiving study treatment.
10. All patients must have a screening head CT and/or MRI to assess for brain metastasis, and subsequently only as clinically indicated. Radiographic tumor assessments (CT or MRI scans) will be obtained to assess extent of disease at the following timepoints: screening (any time within 28-day period of Cycle 1, Day 1) and thereafter tumor assessments should be performed in accordance with the local standard of care while the patient is receiving study treatment. If at any time during the treatment phase there is suspicion of disease progression based on clinical or laboratory findings before the next scheduled assessment, an unscheduled tumor assessment should be performed. If a PET scan is used for preliminary assessment of progressive disease or for SCC follow-up assessment, a corresponding CT scan is required to be completed. A documented standard-of-care tumor assessment performed within 28 days of Cycle 1, Day 1 may be used for the screening assessment (must contain a chest CT scan).

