5.3 Clinical Assessments and Procedures

All patients will be closely monitored for safety and tolerability during all cycles of therapy, at the study completion visit, and during the survival follow-up period. After signing the informed consent, adverse events will be collected as detailed in Section 7.2.1. Patients will be assessed for adverse events weekly during the first two cycles, prior to each subsequent cycle, and as necessary throughout the study. All adverse events will be recorded until 28 days after the last dose of study treatment or until initiation of another anti-cancer therapy, whichever occurs first. Dosing will occur only if the clinical assessment and local laboratory test values are acceptable.

Visits are based on the 28-day cycle. If the timing of a protocol-mandated procedure coincides with a holiday and/or other scheduling conflict that precludes the visit, the visit should be scheduled on the date nearest to the date in question, which may be earlier or later.

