depend on the cohort assignment, with at least 8 hours between doses. Each dose of vemurafenib should be taken with a glass of water. As soon as feasible after signing informed consent, patients previously treated with vemurafenib should continue vemurafenib treatment with study drug provided expressly for this particular study and discontinue their supply of drug derived either from their antecedent vemurafenib study or a pharmacy.

Both cobimetinib and vemurafenib will be taken at the same time in the morning.

On PK sample collection days, patients will be required to come into the clinic and have vemurafenib and cobimetinib administered as part of the scheduled study visit after pre-dose assessments have been performed. Vemurafenib and cobimetinib may be taken with or without food, including on PK sampling days.

Patients will be instructed as to the number and strength of the tablets and/or capsules to take according to their assigned dose cohort. The cobimetinib and vemurafenib tablets and/or capsules should never be chewed or opened.

If a dose is missed (not taken within 4 hours after the scheduled dosing time), the patient should resume dosing with the next scheduled dose. Missed or vomited doses will not be made up.

Patients will be asked to record the time and date they take each dose in a medication diary. Missed doses should be recorded in a patient diary. Patients will be instructed to bring all unused study medication and their medication diaries to each study visit for assessments of compliance.

The protocol requires a study evaluation to occur on Day 1 of every cycle but allows a period of ± 3 days. Patients on the 14/14 and 21/7 dosing schedule of cobimetinib are required to have the minimum number of days per cycle without cobimetinib dosing 14 and 7 days, respectively. Patients are still expected to return for PK blood draws according to the schedule outlined in [Table 10](#) and [Table 11](#). For example, if a patient on a 21/7 cobimetinib dosing schedule has a study evaluation 2 days earlier than the nominal study day, the patient cannot restart cobimetinib until he/she has had at least 7 days without cobimetinib dosing.

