6.1.1 Vemurafenib and Cobimetinib Dose Modification

Dose modifications, interruptions, and delays of vemurafenib and/or cobimetinib study treatment during and after the DLT assessment window should be made on the basis of the guidelines provided in [Table 12](#). Recognizing that new knowledge will be acquired and unforeseen safety issues may arise in the course of the study, the guidelines are not exhaustive and do not represent the full spectrum of care or treatment options described. The dose modification guidelines are not intended to replace clinical judgment or dictate care of individual patients.

Table 12 Vemurafenib and Cobimetinib Dose Modification Guidelines

Adverse Event	Action

A) Rash/desquamation: Grade ≥ 3
	
a) The appearance of rash must be characterized as acneiform or non-acneiform.
 
b) Acneiform rash
 
 • Initiate supportive measures per site guidelines. • Delay cobimetinib dosing until Grade ≤ 2. • Vemurafenib dosing may continue when cobimetinib is interrupted. • Reduce cobimetinib by one dose level (e.g., 60 to 40 mg at assigned dosing schedule). If after restarting at reduced dose, the patient experiences skin toxicity grade ≥ 3, further reduce cobimetinib by another dose level (e.g., 40 to 20mg at assigned dosing schedule). Permanently discontinue cobimetinib if restarting after second dose reduction, the patient experiences skin toxicity grade ≥ 3. • If rash Grade ≥ 3 persists for >28 days despite adequate supportive care, cobimetinib may be resumed if in the investigator's judgement, the benefit-risk of treatment remains favorable. 
c) Non-acneiform, maculo-papular rash
 
 • Initiate supportive measures per site guidelines. • Delay vemurafenib dosing until Grade ≤ 2. • Cobimetinib dosing may continue when vemurafenib is interrupted. • For Grade 3 rash, reduce vemurafenib by one dose level (e.g., 960 to 720 mg or 720 to 480 mg). If after restarting at reduced dose, the patient experiences skin toxicity Grade ≥ 3, further reduce vemurafenib by 1 dose level. Permanently discontinue vemurafenib if restarting after second dose reduction, the patient experiences skin toxicity Grade ≥ 3. • For Grade 4 rash, reduce vemurafenib by two dose levels (e.g., 960 to 480 mg or 720 to 240 mg). Permanently discontinue vemurafenib if after restarting at reduced dose, the patient experiences skin toxicity Grade ≥ 3.

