G) Asymptomatic CPK elevations	
a) Grade ≤ 3: cobimetinib dosing does not need to be modified or interrupted to manage asymptomatic Grade ≤ 3 CPK elevations.
 
b) Grade 4: Interrupt cobimetinib treatment. If improved to Grade ≤ 3 within 4 weeks, restart cobimetinib at a dose reduced by 20 mg, if clinically indicated. Vemurafenib dosing can be continued when cobimetinib treatment is modified, if clinically indicated. If CPK elevations do not improve to Grade ≤ 3 within 4 weeks following dose interruption, permanently discontinue cobimetinib treatment.

H) Liver function test (LFT) elevations	
a) If Grade 1 or 2, continue current dose of vemurafenib and cobimetinib.
 
b) If Grade 3 or 4, hold vemurafenib. Continue current dose of cobimetinib. Upon resolution of LFT to Grade ≤ 1, resume vemurafenib at one lower dose level (e.g., 960 to 720 mg, or 720 to 480 mg).
 
c) If Grade 3 or 4, LFT elevation recurs after one dose reduction, vemurafenib may be reduced by another dose level (e.g., 720 to 480 to 240 mg). Permanently discontinue vemurafenib if Grade 4 LFT elevation recurs when vemurafenib is at a dose of 240 mg bid and continue current dose of cobimetinib.

Table 12 Vemurafenib and Cobimetinib Dose Modification Guidelines (Cont.)

Adverse Event	Action

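### The schedule of assessments does not carry the monthly CPK monitoring rule past Cycle 4

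*Combined protocol and SAP*

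**What the plan says.** Two sections of the current protocol state the monitoring rule in the same sentence. Section 1.3.7.4 gives it as background, and Section 3.10.2.1 repeats it in the safety plan under the identified risks of cobimetinib: "CPK will be monitored at baseline and monthly during treatment or as clinically indicated". Neither names a cycle at which monthly testing stops.

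Table 9 in Section 5 has no separate CPK row. Footnote 7 lists CPK within the chemistry panel and then says: "Frequency of chemistry assessments after Cycle 4 should be performed in accordance with the local standard of care". Its only remark specific to CPK concerns measuring the MB fraction once CPK is already raised.

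The action that depends on the test is in Section 6.1.1, Table 12, row G (asymptomatic CPK elevations). No change is needed up to Grade 3. Above that, the advice is: "Grade 4: Interrupt cobimetinib treatment". The section introduces the whole table as guidance: "The dose modification guidelines are not intended to replace clinical judgment or dictate care of individual patients".

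**The concern.** A site plans its visits and blood draws from the schedule of assessments. If the schedule releases the chemistry panel to local practice after Cycle 4 and says nothing separate about CPK, the monthly rule survives only in narrative sections that a study coordinator may not consult when booking tests.

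What is at stake is detection of a rise that causes no symptoms. A patient with muscle symptoms would be tested on clinical grounds and managed under row F of Table 12. A patient with an asymptomatic Grade 4 value is found only by routine testing, so testing on clinical indication cannot stand in for an interval. The protocol itself lists rhabdomyolysis and CPK elevation as an identified risk of cobimetinib.

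**Working it through.** No formula or stated figure is involved. The check sets every current statement about CPK or chemistry timing side by side and asks whether any of them fixes a CPK interval after Cycle 4.

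1. **Sections 1.3.7.4 and 3.10.2.1.** Monthly on treatment, or when clinically indicated, with no end cycle.
2. **Table 9, footnote 7.** CPK belongs to the chemistry panel. After Cycle 4 the panel follows local standard of care, with no CPK exception. Cycles are 28 days (Section 5.3), so Cycle 4 ends on Day 4 × 28 = 112. After that the footnote states no maximum interval.
3. **Table 9, chemistry row.** A mark appears in the Cycle 4+ area. The extracted grid is broken and its exact column cannot be read reliably. Wherever it sits, footnote 7 governs the frequency after Cycle 4.
4. **Section 5.4.1** lists CPK among the serum chemistries without a frequency. **Section 5.4.2** refers the reader to Table 9.
5. **Section 3.10.3** provides safety monitoring every four weeks from Cycle 3. It does not name CPK, and for laboratory timing it returns to the same table: "specific laboratory studies, including serum chemistries and blood counts (see Section 5.3.4, Table 9 for the list and timing of study assessments".
6. **Section 6.1** sets a visit each cycle: "The protocol requires a study evaluation to occur on Day 1 of every cycle but allows a period of ± 3 days". It does not say that chemistry or CPK is drawn at that visit. Footnote 2 of Table 9, on physical examinations, pulls the other way: "The frequency of each study visit should be performed in accordance with the local standard of care".
7. **Section 5.3** adds a condition on dosing: "Dosing will occur only if the clinical assessment and local laboratory test values are acceptable". Section 6.1 likewise dispenses drug once eligibility to continue has been established. Both presuppose laboratory results, but neither says which tests or how often.

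Items 2 and 4 to 7 either point back to Table 9 or set no CPK interval. There are then two readings of item 1. If monthly is binding, the schedule omits a binding test after Day 112. If the *or* makes monthly optional, no section sets a routine CPK interval after Cycle 4. Either way, a site that follows Table 9 could exceed a month between routine CPK tests.

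DLTs are assessed only in the 28 days of Cycle 1 (Section 3.1.3), and the MTD rules in Section 3.1.4 rest on those DLTs. The gap opens after Cycle 4 and cannot reach either.

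**The case against.** The strongest reply is that the two texts can both be followed. The safety sections allow testing on clinical indication as an alternative to monthly testing. Footnote 7 is a general statement about a whole panel and tells no site to stop monthly CPK, and a site whose local practice is monthly chemistry satisfies both. A patient on treatment is also due an evaluation at Day 1 of each cycle and four-weekly safety monitoring, and dosing depends on acceptable laboratory values. Most CPK elevations are described in Section 3.10.2.1 as asymptomatic, non-serious and resolving with or without interruption, and row G asks for nothing below Grade 4.

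Much of this stands. A reader might infer a flat contradiction, and the documents do not support that: the accurate description is a rule not carried into the schedule. The compatibility argument does not close the gap, however. It depends on local practice, which the documents do not describe, and the mitigating sections either refer back to Table 9 or are silent on CPK.

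A reader might also take the 11.3% of patients with Grade ≥ 3 CPK adverse events on cobimetinib plus vemurafenib in Study GO28141 as the size of the problem. It is not: that figure includes Grade 3, at which row G makes no change when the patient has no symptoms, and it says nothing about when events began.

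**Conclusion.** The point holds as an internal inconsistency that should be corrected. After Cycle 4 the operative schedule does not carry the monthly CPK rule stated in two safety sections, and no other section supplies a CPK interval.

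Its size is unknown. The exposed group is patients on cobimetinib after Cycle 4 who first develop an asymptomatic Grade 4 rise at a site that tests chemistry less often than monthly. The documents give no Grade 4 CPK rate, no onset timing and no account of local practice, so no number can be put on it. A reader might infer that patients will be missed or harmed. The text shows only that the schedule permits longer gaps.

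The conclusion assumes that sites work from Table 9 when booking tests, and that the monthly sentence was meant to apply throughout treatment, as its wording suggests. It is a patient-safety point only, with no effect on the DLT assessment or the choice of MTD.

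**What to change.** Add to Table 9 footnote 7, after the sentence on chemistry frequency: *except CPK, which continues to be measured at the Day 1 evaluation of every cycle (± 3 days) while the patient receives cobimetinib, and additionally as clinically indicated.* In Sections 1.3.7.4 and 3.10.2.1, change *or as clinically indicated* to *and as clinically indicated*.

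Tying the test to Day 1 uses the evaluation and window that Section 6.1 already sets, so no new visit type or separate cap on the interval is needed.

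The cost is one footnote clause, one word in each of two sections, and one local CPK result per cycle after Cycle 4. Sites whose local chemistry is less frequent would need an extra draw. Rewording the two safety sections down to local standard of care would also make the texts agree and would add no tests, but it would give up the routine monitoring that the safety plan describes for an identified risk.
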